1 FLOW CHARTS

1.1 GRAPHICAL STUDY DESIGN

1.2 STUDY FLOW CHART

	Scree traini	ening an ng	d					Treatment Period (15-16 weeks)								Follow up				
Visit Windows: Visit 4 - 19: ± 3 days	1	2*	3	4 ^a ≅	5 ^a	6 ^a	7	8 a	9 ^a	10 ^a	11	12 ⁸	13 ^a	14 ^a	15	16 ^a	17 ^a	18 ^b	19	20 ^a
Week	-4	-3 -1	(R)	1	2	3	4	5	6	7	8	9	10	11	12	13	14	15	16	2+2 days
Informed consent	Χ																			
Inclusion/Exclusion criteria	Χ	Χ	Χ																	
Medical and surgical history; diabetes history	Χ																			
Physical examination, including neuropathy screening	Х																			
Vital signs ^C and Body weight	Χ		Χ				Х				Χ				X				X	
Height	Χ																			
Dispensation/collection of study diary	Χ	Х	Χ				Χ				Χ				Χ			Χ	Х	
Dispensation of study medication			Χ				X				Χ				Χ					
IMP compliance Check; collecting and counting used and unused pens							X				X				X			X	X	
IVRS call	Χ		Χ				Χ				Χ				Χ				Χ	
Randomization			Χ																	
Documentation and review of basal and bolus insulin dose	Х	Х	Х	Х	Х	Х	Х	Х	Х	Х	Х	Х	Х	Х	Х	Х	Х	Х	Х	
Change from BID to QD basal insulin injection (if applicable)		Х																		
CGM, SMPG:										•										
Training and re-training: Glucometer, SMPG profiles, study diary	Х	Х	X				Х				X				X			Х		
Dispensation glucometer,	Χ																			
Dispensation CGM device; Blinded CGM ^d		Χ																Χ		
Upload CGM to PC			Χ			 			 	 			 						Х	
Collect CGM device			Χ							 			 						X	
SMPG ^e	Х	Х	Х	Х	Х	Х	Х	Х	Х	Х	Х	Х	Х	Х	Χ	Х	Х	Х	Х	
Upload SMPG to PC		Х	Χ				Χ				Χ				Χ			Χ	Х	
Concomitant medication	Χ	Х	Χ	Х	Х	Χ	Χ	Х	Х	Χ	Χ	Х	Χ	Χ	Χ	Х	Χ	Χ	Х	Х
Central Laboratory						•			•	•				•			•			
HbA1c, Fasting plasma glucose (FPG)	Χ										Χ								Χ	

Amended Clinical Trial Protocol No. 01 LPS14587 - insulin glargine

02-Aug-2016 Version number: 1

	Scree trainii	ning an ng	d		Treatment Period (15-16 weeks)									Follow up						
Visit Windows: Visit 4 - 19: ± 3 days	1	2*	3	4 ^a	5 ^a	6 ^a	7	8 a	9 ^a	10 ^a	11	12 ^a	13 ^a	14 ⁸	15	16 ^a	17 ^a	18 ^b	19	20 ^a
Week	-4	-3 -1	(R)	1	2	3	4	5	6	7	8	9	10	11	12	13	14	15	16	2+2 days
C-peptide ^f	X																			
Safety Laboratory																				
Hematology ^g , Clinical Chemistry ^h	Х																			
Urine analysis ⁱ	Χ																			
Pregnancy test (WOCBP only) ^j	Χ		Х				Χ				Х				Х				Х	
AE / SAE	To be	assesse	ed and re	eported	(if any) t	hrougho	ut the s	tudy (re	port SAI	E to the	sponsor	within 2	4 hours)						
Injection site reactions, hypersensitivity reactions	To be	To be assessed and reported (if any) throughout the study																		
Hypoglycemia recording	To be	To be assessed and reported (if any) throughout the study																		

^{*} additional screening visits may be needed for patients who cannot handle CGMS at home in order to generate 4 days of useable CGMS data prior to randomization.

- a Telephone visit; Note: Telephone counseling will be available at any time as required.
- b Or early termination visit. Patients who failed to provide 4 days of usable CGM data will be retrained and will repeat the blinded CGM course.
- c Heart rate and blood pressure (sitting position)
- d If a patient fails the first attempt for any reason, he/she will be retrained for CGM conduct and complete another course of blinded CGM.
- e SMPG to be performed by trial patients after Visit 1 and throughout the study duration:
 - 1. Fasting (prebreakfast/preinjection) SMPG: daily until dose optimization has been completed and fasting SMPG goal is reached. Thereafter, the number of fasting SMPG checks can be reduced according to the investigator's judgment, however at least 3 fasting (prebreakfast) SMPG measurements per week should be done.

 Note: after randomization, the pre-breakfast SMPG (including in 5-point and 7-point SMPG profiles) should follow the time window for Pre-injection plasma glucose
 - 2. Pre-injection SMPG (within 30 min prior to injection of Toujeo or Lantus before breakfast) during the 16-week treatment period: at least on 5 days per week during the week prior to each on-site visit after randomization (Visit 7, 11, 15 and 19)) and the SMPG value must be assigned by the patient in the diary
 - 3. 5-point SMPG profile (prebreakfast, prelunch, predinner and 2-hour post a main meal or follow the investigator's instruction and bedtime): at least on 5 days per week throughout the study, starting after Visit 1. Patients should test their 2-hour post meal SMPG after main meals (e.g. lunch or dinner) or follow the investigator's instructions for meal-time insulin titration. Once the titration goal is reached (fasting and 2-hours postprandial SMPG stable in the target range), the number of 5-point SMPG profiles can be reduced according to the investigator's judgment but 5-point SMPG profiles at least on 3 days in the weeks that the5-point SMPG data are collected (section 10.2.3.2) are mandatory.
 - 4. 7-point SMPG profile (before and 2 hours after breakfast, lunch and dinner, and bedtime): at least ONE day during the weeks prior to Visit 3, 15 and 19
- f Only for patients without documented test results to assess the relevant exclusions
- g Hematology: erythrocytes, hemoglobin, hematocrit, leukocytes and platelets
- h Clinical chemistry: total bilirubin (in case of values above the normal range, differentiation in conjugated and non-conjugated bilirubin), AST, ALT, ALP, plasma glucose, creatinine, estimated creatinine clearance, uric acid, sodium, potassium
- i Urine analysis: pH, glucose, ketones, leucocytes, blood/hemoglobin, protein
- j For women of childbearing potential (WOCBP): serum pregnancy test for screening; urine pregnancy test for subsequent monitoring and if needed, it can be confirmed by a serum test.

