10.1.4 Onsite visits (V7, V11, V15 and V18) during treatment period

Four onsite study visits before the end of treatment are scheduled for dispensation of study material and IMP, SMPG data uploading and face-to-face discussion about the patients' progress, SMPG patterns, dose regimens and data collected during the study (eg, hypoglycemia, AE/SAE, average fasting and postprandial SMPGs over the past days).

Patients will bring their glucose meter, diary and IMP boxes to the study site at each visit.

The Investigators and study staff will check and **document in the source data**, if the patient has reached the titration goal or not at each onsite visit. Appropriate titration will be continued until target fasting SMPG without hypoglycemia has been reached.

SMPG data stored in the glucose meter will be uploaded to the study computer via and the report will be available for the investigator to review and source document for tracking patients' SMPG performance and for the titration recommendation.

IMP compliance (collecting and counting used and unused cartridges and syringes and SMPG compliance (pre-injection SMPG, 5 point SMPG) will be checked and addressed with the patients.

Consultation for Diet and life-style modification should be provided during the onsite visits if needed.

Additional assessments will be performed at the specific visits:

- **Visit 11:** patients should be fasted and blood will be drawn for measurements of HbA1c and FPG at central laboratory,
- Visit 15: one day 7-point SMPG will be verified and data collected onto the eCRF,
- **Visit 18:** following will be performed:
 - Dispensation of CGM device and training for CGM conduct if needed,
 - CGM sensor insertion under the supervision of investigator or designees,
 - Patient will start wearing the blinded CGM device for 7 days,
 - The patients should be reminded that the IMP insulin (Toujeo or Lantus) dose should not be changed during the next week while the mealtime insulin dose can still be adjusted appropriately.

For a complete list of procedures scheduled for each study visit please refer to the Study flowchart (Section 1.2).

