10.1.5 End of Treatment (EOT) visit (Visit19, Week 16)

End of Treatment visit (Visit 19) will occur 7 days after Visit 18 when the patients have completed the blinded CGM. If a patient is not able to keep the visit date for any reason, he/she should inform the study site immediately to reschedule the visit as soon as possible. In such a case, the CGM system will automatically stop working and the sensor/transmitter may be removed by the patient at home or at the site later (Section 10.2.4). Before the visit day, patients should be reminded to be fasted for about 8 hours and to bring the CGM device, glucose meter, study diary, used and all unused IMP to the sites. Patient should be reminded **not to inject** the IMP and/or breakfast mealtime insulin at home if applicable since the IMP will be injected at the study site.

At this visit, quality of CGM performance will be assessed before the end of treatment. Investigators will upload the CGM data via DexCom and review the CGM summary to determine the quality of CGM performance (Section 10.2.4.2).

At this visit patients will inject the last dose of IMP which will be given after blood is drawn for laboratory measurements. In addition to all the performances done at each onsite visit, the EOT procedure will include CGM device collection, physical examination and vital signs and endpoint laboratory tests. SMPG will be uploaded, 7-point SMPG checked and all unused IMP collected.

Patients who fail to provide at least 4 days of qualified CGM data will be retrained and repeat the CGM for another week (Section 10.2.4.2). **End of treatment will be delayed accordingly**. All the procedures will be done or redone at the postponed EOT visit.

For a complete list of procedures scheduled for this study visit please refer to the Study flowchart (Section 1.2).

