10.4.5 Procedure and consequence for patient withdrawal from study

The patients may withdraw from the study before study completion if they decide to do so, at any time and irrespective of the reason. Withdrawal of consent for treatment should be distinguished from withdrawal of consent for follow-up visits and from withdrawal of consent for non-patient contact follow-up, eg, medical records check. Patients requesting withdrawal should be informed that withdrawal of consent for follow-up may jeopardize the public health value of the study. If possible, the patients should return for an onsite visit and assessed using the procedure planned for the end-of-study visit (Visit 19).

Patients who withdraw should be explicitly asked about the contribution of possible AEs to their decision to withdraw consent, and any AE information elicited should be documented. Preferably the patient should withdraw consent in writing and, if the patient or the patient's representative refuses or is physically unavailable, the site should document and sign the reason for the patient's failure to withdraw consent in writing.

All study withdrawals should be recorded by the Investigator in the appropriate screens of the e-CRF and in the patient's medical records when considered as confirmed. In the medical record, at least the date of the withdrawal and the reason should be documented.

For patients who fail to return to the site, the Investigator should make the best effort to re-contact the patient (eg, contacting patient's family or private physician, reviewing available registries or health care databases), and to determine his/her health status, including at least his/her vital status. Attempts to contact such patients must be documented in the patient's records (eg, times and dates of attempted telephone contact, receipt for sending a registered letter)

Patients who have withdrawn from the study cannot be rerandomized (treated) in the study. Their inclusion and treatment numbers must not be reused.

The SAP will specify how these patients lost to follow-up for their primary endpoints will be considered.

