2.5.4 Windows for time points

The following process will be applied for visit re-allocation. Re-allocated visits will be used in all statistical analyses (descriptive statistics, graphs, and statistical models).

No re-allocation will be performed for nominal visits already provided in the clinical database (Visit 1 to Visit 20), and for unscheduled assessments.

End of treatment visit

If a patient discontinues the treatment prematurely, end of treatment assessments will be re-allocated to the next scheduled on-site visit for the patient. The next scheduled on-site visit for each patient will be determined as the next on-site visit that should be performed as per protocol, following the last visit actually performed by the patient before end of treatment visit.

For a given parameter, the value will not be re-allocated in the following cases:

- If the parameter is not planned to be collected at the re-allocation visit.
- If a value is already available for the parameter at the re-allocation visit.

This process will be used to retrieve all assessments (including efficacy and safety) performed at the end of treatment visit.

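### Both flow charts place early termination at Visit 18, which has no HbA1c/FPG, vital signs, weight or pregnancy test, while Protocol 10.4.5 asks for the Visit 19 procedures

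*Protocol*

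**What the plan says.** Protocol 1.2 and SAP 1.4 each carry a footnote b on Visit 18 (Week 15): "Or early termination visit. Patients who failed to provide 4 days of usable CGM data will be retrained". The rest of the footnote says that these patients repeat the blinded CGM course.

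Protocol 10.4.5, on withdrawal from the study, says that if possible "the patients should return for an onsite visit and assessed using the procedure planned for the end-of-study visit (Visit 19"). Protocol 10.1.5 describes that visit: "the EOT procedure will include CGM device collection, physical examination and vital signs and endpoint laboratory tests".

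In the Protocol's chart the row "HbA1c, Fasting plasma glucose (FPG") is marked after baseline only at Visit 11 (Week 8) and Visit 19 (Week 16). Section 10.1.4 agrees; for Visit 11 it states that "patients should be fasted and blood will be drawn for measurements of HbA1c and FPG at central laboratory", and it lists no blood draw at Visit 18.

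SAP 2.5.4 moves end-of-treatment assessments of patients who stop early to their next scheduled on-site visit. One exception is "If the parameter is not planned to be collected at the re-allocation visit".

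**The concern.** The two instructions name different visits with different content, so a site cannot follow both for the same patient. Protocol sections 10, 10.1.4 and 10.1.5 send the reader to the flow chart for the full set of procedures at a visit, so the version with fewer assessments is the one a coordinator is likely to use.

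The safety data are affected first. Protocol 11.4.3 summarizes vital signs and weight on the safety population, including the last on-treatment value. That population includes early leavers, and for them the value would come from an earlier visit or not exist. The HbA1c and FPG data are thinned in the same way. HbA1c has some weight in the argument, because Protocol section 4 calls the 4-point difference in time in range clinically relevant on the assumption that HbA1c will be similar in the two arms.

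**Working it through.** **1. The plan's own figure.** SAP 1.3 allows about 15% dropout: 262 / (1 − 0.15) = 308.2 per arm, against 308 stated. Overall, 524 / 616 = 85.1% are expected to be evaluable, so 616 − 524 = 92 are not. These 92 include patients who complete the study but lack four usable CGM days and who still have a Visit 19 HbA1c. The figure is therefore an upper bound on leavers, not an estimate. The documents give no stopping times.

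**2. The two visits side by side** (Protocol 1.2).

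| Procedure | Visit 18 | Visit 19 |
|---|---|---|
| HbA1c, FPG | no | yes |
| Vital signs, body weight | no | yes |
| Pregnancy test (women of childbearing potential) | no | yes |
| IVRS call | no | yes |
| CGM device dispensed | yes | no |
| CGM uploaded and device collected | no | yes |
| Diary, IMP check, insulin doses, SMPG upload, concomitant medication | yes | yes |

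The second sentence of footnote b concerns a patient whose CGM has failed. Protocol 10.1.5 and 10.2.4.2 place that decision at Visit 19, after the upload. This suggests, without proving it, that the marker sits one column too early.

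**3. What an early leaver would have under the Visit 18 reading** (visit windows of ±3 days ignored).

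- Vital signs and weight are planned at Weeks 4, 8, 12 and 16. A patient who leaves before Week 4 has no post-baseline value. After that, the latest value is at most 8 − 4 = 12 − 8 = 16 − 12 = 4 weeks old.
- HbA1c and FPG are planned at Weeks 8 and 16. A patient who leaves before Week 8 has none. After that, the latest value is at most 16 − 8 = 8 weeks old.

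**4. SAP 2.5.4, if the Visit 19 procedures are done.** The on-site visits are those in the section title "Onsite visits (V7, V11, V15 and V18) during treatment period", followed by Visit 19. HbA1c/FPG is planned only at 11 and 19.

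| Last visit performed | Next on-site visit | HbA1c/FPG planned there |
|---|---|---|
| 3–6 | 7 | no |
| 7–10 | 11 | yes |
| 11–14 | 15 | no |
| 15–17 | 18 | no |
| 18 | 19 | yes |

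So the value has no slot when the next on-site visit is 7, 15 or 18, although the section says that its process retrieves all end-of-treatment assessments. For vital signs and weight, the only such case is a next visit of 18.

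**5. Who can enter the HbA1c model.** Protocol 11.3.1.1 defines the mITT by the endpoint of interest. SAP 2.3.1.1 requires enough CGM data for the primary endpoint. Under the SAP, a patient who leaves before the Week 15 CGM is outside the efficacy population, and so outside the HbA1c MMRM, whatever 2.5.4 does with the value.

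**The case against.** The strongest reply is that this is a clerical slip. Section 10.4.5 states the withdrawal procedure expressly, and a sensible site would follow it. Dispensing a CGM device to a departing patient is an extreme literal reading. Patients who stop IMP but stay in the study follow the normal schedule (Protocol 10.4.4) and keep Visits 11 and 19. HbA1c and FPG are other endpoints with nominal p-values (Protocol 9.3, SAP 2.4.4.3), and vital signs and weight are descriptive. All of this stands and limits the consequence. It does not remove the contradiction, since the chart is the document to which sites are repeatedly sent.

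A reader might infer something stronger: that the SAP re-allocation rule drops most early-stop HbA1c values from the MMRM. The documents do not support that, for four reasons.

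- The SAP's mITT already excludes those who leave before the Week 15 CGM, including those whose value 2.5.4 would place at Week 8.
- SAP 2.5.4 does not move records already labelled Visit 1 to Visit 20, and nothing says how an early-termination HbA1c is labelled. Entered as Visit 19, it could be analysed as Week 16.
- A share of patients would need stopping times, which are not given.
- An HbA1c drawn within 7 days of the last dose counts as on-treatment (SAP 2.1.3). It can still supply the last on-treatment value, and patients who stop after Visit 11 already have a Week 8 value.

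Nor does the footnote make the comparison of time in range at similar HbA1c one of completers. The primary analysis excludes withdrawals before Week 15 by stated design (Protocol 9.1, SAP 2.1.3).

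**Conclusion.** The conflict between footnote b and Protocol 10.4.5 is real, appears in both documents' charts, and rests on no assumption. If sites follow the chart, early leavers contribute no end-of-treatment vital signs, weight, pregnancy test, HbA1c or FPG. This weakens the safety-population last on-treatment summaries and the available HbA1c/FPG data. The number of patients cannot be derived from the documents; 92 of 616 is a ceiling. The primary endpoint and the tested hierarchy are not affected.

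The missing slots in SAP 2.5.4 are a secondary observation. The rule falls short of its stated purpose for HbA1c and FPG, but changing it would matter for early leavers only if the analysis population for those endpoints were also endpoint-specific, as in the Protocol.

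**What to change.** Reconcile footnote b with Protocol 10.4.5 by moving the early-termination label from Visit 18 to Visit 19 in the Protocol and SAP flow charts. The cost is one label in each chart. It adds no procedure beyond those 10.4.5 already requests. It should be done while patients are still on study, because measurements not taken cannot be recovered.

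If the sponsor also wants HbA1c/FPG from early leavers in the MMRM, three SAP changes are needed together: return to the Protocol's endpoint-specific mITT for these endpoints, state how early-termination records are labelled, and say which visit they are assigned to. The last has a price. Sending a value to the next visit at which HbA1c is planned would label a Week 9 value as Week 16, 16 − 9 = 7 weeks later than it was drawn. Leaving 2.5.4 as it is, with its wording limited to what it does retrieve, is also defensible.

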3 LIST OF ABBREVIATIONS

AE: adverse event

AESI: adverse event of special interest

ALP: alkaline phosphatase
ALT: alanine aminotransferase
AST: aspartate aminotransferases
CGM: continuous glucose monitoring

DBP: diastolic blood pressure
DRF: discrepancy resolution form
e-CRF: electronic case report form
FPG: fasting plasma glucose
GCP: good clinical practice

GFR: estimated glomerular filtration rate

HbA1c: glycated hemoglobin A1c HGLT: high group level term

HLT: high level term

ICH: International Conference for Harmonisation

IEC: independent ethics committee
IMP: investigational medicinal product

IRB: institutional review board

IVRS: interactive voice response system IWRS: interactive web response system

LLT: lower level term

MedDRA: Medical Dictionary for Regulatory Activities

mITT: modified Intent-to-Treat

NIMP: non-investigational medicinal product

NPH: neutral protamine Hagedorn

PT: preferred term

PTC: product technical complaint

RR: rate ratio

SBP: systolic blood pressure

SC: subcutaneous

SMPG: self-monitoring plasma glucose

SOC: system organ class

USPI: United States package insert WOCBP: women of childbearing potential

4 INTRODUCTION AND RATIONALE

Insulin glargine (HOE901) is a recombinant analog of human insulin providing a 24-hour (h) basal insulin supply after a single-dose subcutaneous (SC) injection. Insulin glargine U100/mL formulation has been marketed as Lantus for 15 years (1). Its efficacy and safety are well-known through extensive data collection involving over 100 000 patients in clinical studies, including randomized, controlled clinical trials and the results of postmarketing surveillance arising from approximately 30 million patient-years of clinical experience.

HOE901-U300 has the same composition as the current Lantus formulation 100 U/mL with adjustment of 3-times the amount of active pharmaceutical ingredient (insulin glargine) and corresponding zinc content and is also approved as Toujeo for once daily injection (2).

Further information on Lantus and Toujeo, including important clinical trials performed pre and post-registration, can be found in the national product labels and Investigator's Brochure HOE901 (3).

As evidenced in previous euglycemic clamp studies (PKD10086, PKD11627 and TDR11626) after a single dose or multiple doses in healthy subjects or patients with Type 1 diabetes (T1DM), there are differences between Lantus and Toujeo in Pharmacokinetics (PK) and Pharmacodynamics (PD) profiles (3). In those euglycemic clamp studies, Glargine -U300 (Gla-U300), as compared to glargine-U100 (Gla-U100), showed less variability to the average concentration, displayed a flatter PK profile, and correspondingly less fluctuation in the glucose lowering activity. Given these features of the PK/PD profiles, Toujeo is considered to be well suitable for constant, peak less 24-hour basal insulin supply in diabetes management, with the expectation of less hypoglycemic risk at equal to tighter blood glucose control.

Clinical implication of Toujeo in management of type 1 diabetes was investigated in clinical studies in patients with T1DM. The EDITION-4 phase 3 trial in patients with T1DM showed similar therapeutic efficacy between Gla-300 and Gla-100 with respect to glucose lowering, while a slightly lower risk of hypoglycemia was observed for Gla-300 (4). PDY12777 was a small-scale (59 patients divided into 4-treatment arms) exploratory study using continuous glucose monitoring system (CGM), which provided sufficient data for diurnal glucose patterns associated with Gla-U300 or Gla-U100 treatment. CGM analysis in participants with T1DM showed better glucose stability and lower intra-patient glucose variability with Gla-U300 than Gla-100. These differences were more evident with the morning injection regimen. Moreover, the incidence of confirmed or severe hypoglycemic events was numerically lower with Gla-300 than with Gla-100. However, neither of the two studies was sufficiently powered to demonstrate reduced rates of hypoglycemia with Gla-300.

The present study LPS14587 is designed to further explore differences between Toujeo and Lantus with the hypothesis that Toujeo, compared to Lantus, given as the basal insulin to patients with T1DM will provide a better continuous glucose profile with less, in particular nocturnal hypoglycemia while the conventional glycemic control as measured by HbA1c is anticipated to be similar between the two treatments.

Amended Clinical Trial Protocol No. 01 LPS14587 - insulin glargine 02-Aug-2016 Version number: 1

This is a randomized, active-controlled, 16-week open-label study to compare the efficacy of Toujeo with Lantus using CGM glucose profiles, sampling ambulatory glucose level every 5-minutes over at least 7 days at baseline and at endpoint (Week 15 or 16). CGM during screening and end of study period (Week 15 or 16) will be blinded to both the investigators and patients.

Eligible patients will be randomized to either Toujeo or Lantus, both given once-daily by subcutaneous (sc) injection in the morning. Patients will be required to titrate their basal and meal-time insulin to achieve the fasting and 2-hours post-prandial SMPG targets during the first 15 weeks of treatment. The CGM will then be performed during Week 15 or 16 during which period, basal insulin doses will be stable without changes.

The primary objective of the study is to demonstrate a greater percent of time in target CGM glucose range of 70-180 mg/dL with Toujeo than Lantus treatment. The main secondary objective is to evaluate the incidence and rate of hypoglycemia and possibly to show a lower rate of documented nocturnal symptomatic hypoglycemia with Toujeo versus Lantus. In addition, all hypoglycemia incidence and distribution (24 hours and nocturnal) will be analyzed according to the ADA classification (severe, documented symptomatic, asymptomatic, probable and relative) (5). Glucose stability and variability will be assessed between and within each group via measurements of diurnal glucose exposure, rate of change in median curve, interquartile range (IQR), mean and variation in glucose profiles, etc (6, 7).

A relatively homogenous patient population will be selected, reducing potential confounding effects, so that the true differences in the therapeutic effects of Toujeo versus Lantus can be assessed. The study population includes patients 18-70 years of age with T1DM, on a basal plus mealtime insulin regimen for at least 1 year, and glycated hemoglobin A1c (HbA1c) level >6.5 and < 10%. Lack of endogenous insulin production (C-peptide) is required to confirm type 1 diabetes (8). Patients must be on a stable dose of long-acting insulin analog basal/bolus regimen for 3 months before study entry. Furthermore, the number of prior hypoglycemia episodes is specified to include patients with known hypoglycemia that may benefit more from treatment with Toujeo.

Approximately 616 patients will be enrolled aiming for at least 524 (85%) evaluable patients, which will provide over 90% statistical power to demonstrate superiority with 4% margin of Toujeo over Lantus for the primary endpoint analysis. The 4% difference in the percentage of time glucose within the target range of 70-180 mg/dL is considered clinically relevant given the assumption that the HbA1c will be similar between the two treatments.

